#### Study Design

This will be a single-center, double-blinded randomized controlled study. The study is comparing blood loss and postoperative pain and swelling in two cohorts: patients undergoing BTB ACL reconstruction who receive TXA during surgery and patients who do not receive TXA. The intravenous tranexamic acid will be administered before surgery begins and after the tourniquet is released at the conclusion of the surgery. Blood loss will be measured via measuring the amount of blood in the drain at the conclusion of the surgery. Patients will be asked on postoperative day 1, 2 and 7 to rate their pain according to the VAS scale. Patients will have their knee swelling measured immediately postoperatively and at their one-week follow up visit. The swelling ratio is defined as the postoperative mean circumference of upper pole of patella and lower pole of patella divided by the preoperative values.[9]

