#### Secondary Objective

Secondary objective of the study is to determine is there is a difference in post operative pain and swelling between patients undergoing BTB anterior cruciate ligament reconstruction who receive TXA and patients who do not receive it.

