#### Version 2/26/20

medical histories will be performed based on their electronic medical records to identify any current pain medications or exclusion criteria. In order to maintain the blind, the resident assisting the surgeon will randomize the patient to one of two cohorts using REDCap. Both the resident and surgeon are members of the study team.

- Cohort 1: 1 gram of intravenous tranexamic acid (TXA) before tourniquet inflation and 1 gram of IV TXA before closure of the incision
- Cohort 2: Will not receive TXA.

The resident physician and anesthesiologist will not be blinded to the study, however the surgeon and study team members will remain blinded. Before the surgery begins, the resident will prepare the patient and the TXA will be administered (if assigned) before the tourniquet is placed, at which point the surgeon will be called into the room. The administration of TXA will not prolong the surgery and will not add any additional risks of prolonged anesthesia The surgeon will exit the surgery before closure at which point, the TXA will be administered (if assigned) and the resident physician will close the incision.

Immediate post-operative management will not be affected by this study. All patients will receive a standardized regimen of aspirin for DVT prophylaxis and Percocet for pain management, which is standard of care post-operative treatment.

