Information to be recorded pre-operatively includes age, sex, height, weight, BMI, and American Society of Anesthesiology (ASA) classification. Intra-operative information will also be recorded, including operative time, and estimated blood loss. During the surgery, a suction device is utilized to remove excess blood from the surgical site and sucked into the suction drain and placed into a measuring cup. We will measure the perioperative blood loss by looking at the measuring cup and seeing how much blood is inside. The objective is to have the average blood loss of the cohort receiving TXA less than the cohort not receiving TXA. Knee swelling postoperatively will be measured using the swelling ratio. The swelling ratio is defined as the circumference of the operative limb divided by the circumference of the contralateral limb. Pain severity scores at rest will be assessed by use of a visual analog scale (VAS; 0 = no pain, 10 =worst pain imaginable) at 0.5, 1, 1.5, 2, 4, 6, 24, and 48 hours as well as 7 days after surgery. Percocet consumption will be recorded at 24 hours, 1 day, 2 days and 7 days after surgery. Incidence of TXA-related side effects (nausea/vomiting, itching, anxiety, increased thirst, rapid heartbeat) in the first 24 hours will be noted. Time to discharge from the post-anesthesia care unit (PACU) and time to discharge from the hospital will be recorded. Patients will be in the study a duration of two weeks, until their post-operative follow up visit.

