#### **Data Analysis and Statistical Plan**

Statistical analysis will be performed using chi-squared and/or fisher's exact testing depending on size for binary variables. An a priori power analysis was conducted to estimate the minimum sample size needed to achieve 83% power (1 - b) at the .05 significance level which was calculated to be 50 patients. Therefore, we added 10 patients to account for potential exclusions, totaling 110 patients. Variables used in the power calculation were taken from the literature including an assumed effect size of 0.5 and standard deviation (SD) of 2. This large sample size will provide enough information to truly determine a difference between cohorts. This sample size and statistical analysis was used in similar studies looking at the effects of TXA in ACL

Version 2/26/20

reconstruction[5, 12].

Continuous variables will be compared with paired t-tests if the data is approximately normally distributed. If the data is not normally distributed, Mann-Whitney tests will be used. All protected health information will be removed prior to statistical analysis. We will use patient subjective pain, perioperative blood loss and knee swelling data as statistical endpoints. Subjective pain will be measured with the VAS (visual analogue scale), perioperative blood loss will be measured looking at blood loss from the suction drain after surgery. We are looking for a statistically significant difference in perioperative blood loss between the two cohorts. The swelling ratio is defined as the postoperative mean circumference of upper pole of patella and lower pole of patella divided by the preoperative values according to our previous study[9]. The endpoints must be statistically significant between the two cohorts to show TXA is effective.

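### Every VAS pain score follows surgery and both TXA doses, so the secondary pain comparison cannot be adjusted for baseline pain; the cost is some precision, not bias.

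*Combined protocol and SAP*

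**What the plan says.** The Secondary Objective asks whether there "is a difference in post operative pain and swelling between patients undergoing BTB anterior cruciate ligament reconstruction", and the Data Analysis and Statistical Plan lists subjective pain on the VAS among the statistical endpoints.

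The pre-operative data are described in section III (Methods and Procedures): "Information to be recorded pre-operatively includes age, sex, height, weight, BMI, and American Society of Anesthesiology (ASA) classification". The same section schedules the resting VAS "at 0.5, 1, 1.5, 2, 4, 6, 24, and 48 hours as well as 7 days after surgery". Study Design gives a different schedule: "Patients will be asked on postoperative day 1, 2 and 7 to rate their pain according to the VAS scale".

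On treatment timing, section III gives cohort 1 "1 gram of intravenous tranexamic acid (TXA) before tourniquet inflation and 1 gram of IV TXA before closure of the incision". Study Design describes the second dose differently, as following tourniquet release at the end of surgery.

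The only pre-operative item related to pain is a chart review, done "to identify any current pain medications or exclusion criteria". Current pain medication is not among the Exclusion Criteria.

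For the analysis: "Continuous variables will be compared with paired t-tests if the data is approximately normally distributed". Mann-Whitney is the alternative for non-normal data. No covariate-adjusted model is mentioned for any endpoint.

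**The concern.** Patients may come to surgery with different levels of knee pain, and the protocol itself expects some to be taking pain medication. If pre-operative pain predicts post-operative pain, a baseline score would explain part of the between-patient variation. Without it, that variation stays in the error term, and a chance difference between cohorts in starting pain can be neither seen nor adjusted for.

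The plan is also uneven. Swelling is referred either to the patient's own pre-operative measurement (Study Design; Data Analysis and Statistical Plan) or to the other limb (section III), while pain has no reference value. A pre-treatment score that is not collected before surgery cannot be recovered later.

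At stake is the precision of the secondary pain comparison. The primary blood-loss comparison is not affected.

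**Working it through.** **Inputs from the documents.** 55 per cohort (Number of Subjects). SD 2, effect size 0.5, 83% power and significance level 0.05 (Data Analysis and Statistical Plan); the endpoint, units and sidedness behind these are not stated.

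**Assumed inputs.** The SD of 2 applies to VAS. The correlation r between pre- and post-operative VAS is not in the documents and is varied from 0.1 to 0.5.

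**Step 1: the plan's own power figure.** The stated 50 patients must mean 50 per cohort, since 2 × 50 + 10 = 110. For a standardised effect of 0.5, the expected z is 0.5 × √(50/2) = 2.5.
- Two-sided: Φ(2.5 − 1.96) = 70.5%.
- One-sided: Φ(2.5 − 1.645) = 80.4%.
- Raw difference 0.5 with SD 2 (standardised 0.25), two-sided: Φ(1.25 − 1.96) = 23.9%.

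None gives 83%. The nearest match is one-sided with 55 per cohort, Φ(0.5 × √(55/2) − 1.645) = 83.6%, but 55 is the number after the allowance for exclusions. The present point does not depend on this figure.

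**Step 2: timing.** The earliest VAS is 0.5 hours after surgery (section III) or day 1 (Study Design). The second dose is given before closure (section III) or at the end of surgery (Study Design). Under every combination, both doses precede the first score.

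**Step 3: precision.** Unadjusted, the standard error of the difference is 2 × √(2/55) = 0.381, so the 95% half-width is 1.96 × 0.381 = 0.75 points. Adjustment for baseline multiplies the error variance by 1 − r² and the half-width by √(1 − r²). The patient ratio is 1/(1 − r²): the unadjusted patients needed to match one adjusted patient.

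| r (assumed) | Variance removed, r² | Half-width multiplier | 95% half-width (points) | Patient ratio |
|---|---|---|---|---|
| 0.1 | 1% | 0.995 | 0.74 | 1.01 |
| 0.2 | 4% | 0.980 | 0.73 | 1.04 |
| 0.3 | 9% | 0.954 | 0.71 | 1.10 |
| 0.4 | 16% | 0.917 | 0.69 | 1.19 |
| 0.5 | 25% | 0.866 | 0.65 | 1.33 |

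The percentages do not depend on the SD; the half-widths scale with it.

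**Step 4: chance imbalance.** If baseline VAS also has SD 2, a baseline difference of 1.96 standard errors is 0.75 points. With equal SDs, the slope of post-operative on baseline VAS equals r, so the post-operative difference shifts by r × 0.7475: 0.22 points at r = 0.3 and 0.37 at r = 0.5.

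**Step 5: power, as an illustration.** For a standardised pain difference of 0.5, 50 per cohort, two-sided, power is Φ(2.5/√(1 − r²) − 1.96): 70.5% unadjusted, 74.6% at r = 0.3 and 82.3% at r = 0.5.

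**The case against.** The strongest reply is that little is lost. Allocation is randomised, so an unadjusted comparison of independent groups is unbiased, and its standard error already allows for chance differences in starting pain. That stands. A reader might infer from the missing baseline that the pain comparison is biased or its error rate uncontrolled; the documents do not support this.

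A reader might also infer that a 0.75-point chance difference at baseline would pass whole into the result. That would need a slope of 1. At r of 0.3 to 0.5 with equal SDs, the shift is 0.22 to 0.37 points.

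Three further objections stand in part:
- The pre-operative list is introduced as what is included, so it may be incomplete; the pre-operative knee circumference needed for one definition of the swelling ratio is not in it either. The list alone does not prove that no score is taken. The two explicit VAS schedules, both wholly post-operative, carry the point.
- The documents give no correlation. One value need not hold from 0.5 hours to 7 days under a standard analgesic regimen, and at r of 0.1 to 0.2 the gain is only 1% to 4% of the variance.
- A baseline score alone would change nothing, because no adjusted analysis is planned and no main pain time is chosen. The measurement and the model must be added together. Calling the t-tests paired does not supply a baseline: with no pre-operative VAS, no change from baseline can be formed.

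The chart review offers a rough proxy for baseline pain, but medication use is not a pain score.

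**Conclusion.** The point holds as a loss of precision on a secondary endpoint. No pre-treatment pain score is scheduled, and the planned analysis has no adjustment. The variance that adjustment could remove is 1% to 25% over an assumed r of 0.1 to 0.5, with 9% at 0.3. On the VAS this means a 95% half-width of about 0.71 points (r = 0.3) or 0.65 (r = 0.5) in place of 0.75, if the SD of 2 applies to VAS and 55 per cohort are analysed.

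The analysis section says that the endpoints must reach significance for TXA to be shown effective, and a reader might infer that this gap undermines the trial's main conclusion. The documents do not support that: the primary objective is blood loss, which is untouched, and the effect on pain is a modest widening of the interval. The priority is low. The case for acting is that the change is cheap and the measurement cannot be made afterwards.

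**What to change.** 1. In section III, add a resting VAS to the pre-operative list, taken in both cohorts before randomization and before the first dose.
2. In the Data Analysis and Statistical Plan, specify that post-operative VAS is analysed by ANCOVA, or by a repeated-measures model over the scheduled times, with baseline VAS as a covariate. Current pain-medication use from the planned chart review may be added as a second covariate.
3. Reconcile the VAS schedules in Study Design and section III, and name the main pain time point. The two descriptions of the second dose's timing also need to be reconciled.

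The cost is one extra question and one REDCap field per patient, and a short addition to the analysis section. Patients already enrolled would lack the value, so the plan should state how they are handled.

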#### **Primary Objective**

The primary objective of the study is to determine if there are any differences in blood loss between patients undergoing BTB anterior cruciate ligament reconstruction who receive TXA compared to patients who do not receive it.

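### Blood loss is compared without adjustment although age, sex and weight are already recorded before surgery: a missed chance of modest precision, not an error

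*Combined protocol and SAP*

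**What the plan says.** The Primary Objective is a between-cohort comparison: "The primary objective of the study is to determine if there are any differences in blood loss between patients undergoing BTB anterior cruciate ligament reconstruction".

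Section III, Methods and Procedures, lists the baseline data: "Information to be recorded pre-operatively includes age, sex, height, weight, BMI, and American Society of Anesthesiology (ASA) classification". Earlier in the same section, a chart review of medications and past "medical histories will be performed based on their electronic medical records to identify any current pain medications or exclusion criteria" is described. Randomisation is through REDCap, and no stratification factor is named.

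The Data Analysis and Statistical Plan is the whole of the analysis plan. For continuous endpoints it says: "Continuous variables will be compared with paired t-tests if the data is approximately normally distributed". The fallback is: "If the data is not normally distributed, Mann-Whitney tests will be used". Binary variables get chi-squared or Fisher tests. No regression model, covariate or stratified analysis is named for any endpoint, and the documents do not say what the baseline variables are for.

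**The concern.** The trial collects patient characteristics before treatment that may be related to how much a patient bleeds. If they are related, leaving them out of the primary analysis keeps explainable variation in the error term, which widens the confidence interval and lowers power. Any chance imbalance between the cohorts on these factors also stays in the estimate. With no stratification named, neither the design nor the analysis makes use of them.

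This matters more when power is short. On the most favourable two-sided reading of the plan's own inputs, 50 per cohort falls well below the stated 83%. Such a plan has reason to use information it already holds, provided that the cost of doing so is counted.

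**Working it through.** **Inputs.**
- From the Data Analysis and Statistical Plan: "83% power (1 - b) at the .05 significance level which was calculated to be 50 patients", and "an assumed effect size of 0.5 and standard deviation (SD) of 2". I read 50 as per cohort, because 2 × 50 + 10 = 110.
- Sidedness is not stated. The Primary Objective asks about any difference, so I use two-sided 0.05. Methods and Procedures is directional ("The objective is to have the average blood loss of the cohort receiving TXA less than the cohort not receiving TXA"), so one-sided figures are given once below.
- The effect size is not tied to blood loss. It may be standardised (d = 0.5) or raw (d = 0.5/2 = 0.25). Both are shown.
- R², the share of blood-loss variance explained by the covariates, is not in the documents. I assume a range of 0 to 0.30.

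**The plan's own figure.** For n per cohort, the two-sample t-test has noncentrality λ = d√(n/2) on 2n − 2 df. With d = 0.5 and n = 50, λ = 0.5 × √25 = 2.5 on 98 df, which gives 69.7% two-sided power (79.9% one-sided). Two-sided power of 83% needs 69 per cohort. The nearest match to 83% is one-sided with 55 per cohort (83.2%), which is the full enrolment with nothing left for exclusions. So 83% at 50 per cohort does not reproduce, and 69.7% is the reference below.

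**Adjusted analysis with k = 3 covariates (sex, age, weight).** Adjustment multiplies the variance of the estimated difference by (1 − R²), and estimating the covariate effects inflates it by (2n − 3)/(2n − k − 3) = 97/94 = 1.032. Hence

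λ = d√(n/2) × √(94/97) / √(1 − R²), on 2n − 2 − k = 95 df.

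The equivalent unadjusted n per cohort is 50/(1 − R²) × 94/97. The relative standard error is √((1 − R²) × 97/94); it does not depend on d.

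| Analysis | λ (d = 0.5) | Power | Equivalent n per cohort | Relative standard error |
|---|---|---|---|---|
| Unadjusted | 2.500 | 69.7% | 50 | 1.00 |
| R² = 0 | 2.461 | 68.3% | 48 | 1.02 |
| R² = 0.05 | 2.525 | 70.5% | 51 | 0.99 |
| R² = 0.10 | 2.594 | 72.8% | 54 | 0.96 |
| R² = 0.20 | 2.752 | 77.7% | 61 | 0.91 |
| R² = 0.30 | 2.942 | 82.9% | 69 | 0.85 |

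**Break-even.** The variance is unchanged when (1 − R²) × 97/94 = 1, that is R² = 1 − 94/97 = 0.031. With five or six covariates the same formula gives 1 − 92/97 = 0.052 or 1 − 91/97 = 0.062.

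**Raw reading (d = 0.25).** Unadjusted λ = 1.25 gives 23.6%. With three covariates, power is 25.0% at R² = 0.10 and 30.7% at R² = 0.30.

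**The case against.** The strongest reply is that nothing here is wrong. An unadjusted comparison of two randomised cohorts is unbiased, and its type I error already allows for chance imbalance. Recording age, sex and body size does not commit a trial to modelling them. That stands in full: a reader might infer that the planned analysis is biased or invalid, and the documents do not support that.

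The second reply is that the benefit is conjectural. Nothing in the documents says that age, sex or weight predicts the blood collected by suction in an operation done with a tourniquet. This also stands. It is why the range must include R² = 0, where adjustment loses 1.4 points (69.7 − 68.3).

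Third, a reader might infer that all the listed variables could be entered and the precision recovered for free. That does not hold. Height, weight and BMI are redundant, every term costs precision at about 100 patients, and break-even roughly doubles if five or six are entered.

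Fourth, the Mann-Whitney fallback takes no covariates, so a linear model displaces the plan's only provision for non-normal data. This is a fair criticism of adjustment proposed without a rule for skewness.

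Fifth, pre-operative analgesic use looks like a ready covariate for pain. But the chart review only says that current pain medications will be identified; they are not in the list of recorded data.

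What survives is narrow: with a small set of covariates fixed in advance, the possible loss is small and the possible gain is larger.

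**Conclusion.** The point holds as an inexpensive improvement. The baseline values are recorded, the analysis plan uses none of them, and a three-covariate model would change two-sided power at 50 per cohort by between −1.4 points (R² = 0) and +13.2 points (82.9 − 69.7, R² = 0.30) if d = 0.5. At R² = 0.10 the gain is 3.1 points (72.8 − 69.7). These figures rest on an assumed R², on reading 50 as per cohort, on two-sided testing, and on 0.5 being standardised. If 0.5 is a raw difference, the trial stays badly underpowered with or without adjustment.

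A reader might infer from the last row of the table that adjustment restores the stated 83%. The documents do not support that: it would take an R² of about 0.30, for which they offer no evidence. Nor does adjustment repair two more serious problems in the same section, a paired test named for independent cohorts and a sample size that does not reproduce. Those need their own corrections and rank above this one.

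**What to change.** In the Data Analysis and Statistical Plan:

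1. Make the primary analysis a linear model of blood loss on cohort, adjusted for sex, age and weight, named in advance. Use weight as the only body-size measure. Report the adjusted mean difference with its 95% confidence interval.
2. Fix in advance how skewed blood loss is handled, for example robust standard errors or a log transformation. Robust standard errors keep the mean difference as the estimate; a log transformation turns it into a ratio, and the plan should then say so.
3. Keep an unadjusted independent-samples comparison as a sensitivity analysis.
4. Do not adjust for operative time, which is determined after the first TXA administration and so is not a baseline variable.
5. Adjust pain for pre-operative analgesic use only if that is added as a recorded data item.

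Cost: wording only, with no new data for sex, age and weight. The statistical price is three of 98 degrees of freedom, or about 1.4 points of power at d = 0.5 if the covariates turn out to explain nothing. The section has to be rewritten in any case to remove the paired test.

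### Pain is scored at up to nine times, but no time, summary, model or multiplicity rule is fixed for the single pain question

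*Combined protocol and SAP*

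**What the plan says.** The Secondary Objective asks one question about pain, jointly with swelling: to "determine is there is a difference in post operative pain and swelling" between the cohorts.

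The protocol gives two pain schedules:

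- Section III, Methods and Procedures, has resting VAS recorded "at 0.5, 1, 1.5, 2, 4, 6, 24, and 48 hours as well as 7 days after surgery", which is nine assessments.
- Section I, Study Design, has three: "Patients will be asked on postoperative day 1, 2 and 7 to rate their pain according to the VAS scale".

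The Data Analysis and Statistical Plan makes pain an endpoint ("We will use patient subjective pain, perioperative blood loss and knee swelling data as statistical endpoints") and gives one rule for all continuous data: "Continuous variables will be compared with paired t-tests if the data is approximately normally distributed". The fallback is: "If the data is not normally distributed, Mann-Whitney tests will be used". It then ties the conclusion to significance: "The endpoints must be statistically significant between the two cohorts to show TXA is effective".

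The section does not choose a pain time, define a mean or area under the curve, specify a model for repeated scores, or adjust for multiple tests.

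**The concern.** One question is asked, but as many as nine answers can be produced, and nothing fixes in advance which of them counts. The significance rule cannot be applied to pain as written, because it does not say at which time, or at how many times, the difference must be significant. Any single significant time could be reported as a pain benefit, at an error rate above the nominal 5%.

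Two further losses follow if each time is tested alone. Scores from the same patient are not combined, so precision is lost when an effect is sustained. A patient with a missed score also drops out of the comparison at that time. The documents give no basis for saying which times will be missed most.

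**Working it through.** **Plan's own figure.** There is none for pain. The sample-size paragraph does not tie its effect size to any endpoint.

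**Inputs from the documents.** Nine times (Methods and Procedures) or three (Study Design); 55 patients per cohort (Number of Subjects); significance level 0.05 (Data Analysis and Statistical Plan), taken as two-sided because sidedness is not stated.

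**Assumptions.** The between-time correlation ρ is not in the documents; 0.3 to 0.9 is used, equal for all pairs of times. For power, a 0.4 SD effect is assumed. The t-test is taken as the two-sample form. The paired form named in the plan does not suit two independent cohorts, which is a separate issue.

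**1. Chance of at least one false-positive time.** With independent tests this is 1 − 0.95⁹ = 0.370 for nine times and 1 − 0.95³ = 0.143 for three. With correlated scores it was simulated (400,000 draws of multivariate normal test statistics):

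| ρ | Nine times | Three times |
|---|---|---|
| 0 | 37.0% | 14.3% |
| 0.3 | 32.6% | 13.6% |
| 0.5 | 27.0% | 12.6% |
| 0.7 | 20.2% | 10.9% |
| 0.9 | 12.4% | 8.4% |

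If correlation instead fades with distance in visit order (first-order autoregressive), the nine-time figures for ρ from 0.3 to 0.9 are 35.7%, 32.9%, 27.6% and 17.3%.

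**2. Precision of the nine-time average.** Its variance relative to one time is (1 + 8ρ)/9. This is 5/9 = 0.556 at ρ = 0.5 and 6.6/9 = 0.733 at ρ = 0.7.

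**3. Power for a sustained 0.4 SD effect, 55 per cohort.**

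- One prespecified time, tested at 0.05: 55%.
- Nine-time average: the standardised effect becomes 0.4/√0.556 = 0.537, power 80% (ρ = 0.5); or 0.4/√0.733 = 0.467, power 68% (ρ = 0.7).
- Any of nine times at the Bonferroni level 0.05/9 = 0.0056 (|z| > 2.77, mean z = 0.4 × √(55/2) = 2.10 at each time; simulated, normal approximation): 67% (ρ = 0.5) or 56% (ρ = 0.7).

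**4. Power if the 0.4 SD effect appears only at 24 h, 48 h and day 7.** Six of the nine times lie at or before 6 hours, so an equal-weight average gives them 6/9 of the weight. The averaged effect falls to 0.4 × 3/9 = 0.133 SD.

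- Equal-weight nine-time average: 0.133/√0.556 = 0.179, power about 16% (ρ = 0.5); 0.133/√0.733 = 0.156, power about 13% (ρ = 0.7). These use the normal approximation.
- Any of nine times with Bonferroni: 48% or 42%.
- Average over those three times only: variance ratio (1 + 2ρ)/3 = 0.667 or 0.8, standardised effect 0.490 or 0.447, power 72% or 64%.

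**The case against.** **The plan does not state separate tests.** This stands. A two-group test on a mean, an area under the curve or one chosen time would also fit the wording. What is established is that no choice has been made, and that no method combining the times is offered.

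**The schedule may have only three times.** The documents conflict, so nine cannot be treated as settled. With three times the problem is smaller but remains: 8.4% to 14.3% over the correlations shown.

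**Pain is secondary.** This stands. The blood-loss test is unaffected. The significance rule may also mean that every endpoint must be significant, in which case an overall effectiveness claim could not rest on one pain time. A separate pain claim would still be open to selection.

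**Multiplicity correction costs little.** A reader might infer that correcting nine tests destroys the power, because one named time at 0.05/9 has only 24% power against 80% for the average. That comparison is not like for like. The question is whether pain differs at all, and the chance that some time passes Bonferroni is 67% at ρ = 0.5, which exceeds the 55% of a single unadjusted test. The average gains about 12 to 13 points for a sustained effect.

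**Averaging can hide a late effect.** This is the strongest objection to a careless fix, and it stands. For an effect from 24 hours on, an equal-weight average does much worse than nine Bonferroni tests (16% against 48% at ρ = 0.5). It is a reason to set the window or weights with care, not to leave the contrast undefined.

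**Other methods would serve.** A prespecified area under the curve, one key time or a Holm procedure would also control the error. The mixed model's advantage is that it also uses patients with some missed scores.

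**Conclusion.** The concern holds as a gap in the specification of the secondary pain analysis. If the times were tested one by one without adjustment, the chance of at least one false-positive pain result would be 37% under independence, about 27% at correlation 0.5 and 20% at 0.7 with nine times, and about 11% to 14% with three times at correlations 0.7 to 0.3. The correlations are assumptions, and 37% is the independence reference rather than the expected value. Even at 0.9 the rate stays above 5%.

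A reader might take the 37% as the trial's overall error rate. The documents do not support that: blood loss is the primary objective and has its own comparison.

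The power gain from a single contrast is real but conditional. It assumes a roughly sustained effect and depends on the weights. Control of the pain error rate by a single prespecified test does not depend on either.

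**What to change.** 1. Reconcile the pain schedules in Study Design and in Methods and Procedures.
2. In the Data Analysis and Statistical Plan, analyse VAS with one mixed model for repeated measures: cohort, time, cohort-by-time interaction and within-patient correlation.
3. Prespecify one cohort contrast as the single pain test at 0.05, and state its time window or weights before analysis. Choose them to match the pain question, for example a time-weighted average (area under the curve) or the window from 24 hours to day 7.
4. Report time-specific differences with confidence intervals as descriptive.
5. Say what replaces the Mann-Whitney fallback for this bounded 0 to 10 scale, for example a Mann-Whitney test on the same per-patient weighted summary as a sensitivity analysis.

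The cost is a paragraph of text and one standard model, with no added patients, visits or data. The price is that an effect confined to times outside the chosen window, or given little weight, will appear only in the descriptive estimates.
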